covered in this IND application. That IRB trial would allow up to five years follow up on subjects and would only allow investigators to observe how the subject is doing long term, whichever treatment options the subject pursues in consultation with their regular doctor in that time. That planned follow up protocol will allow Stanford to contact the subjects several times a year in order obtain information about any therapy they may elect to follow, including sildenafil if their regular doctor prescribes it, and their response to any therapy.

Multi-Center:

Yes

Number of Centers:

Up to 4

Blinding:

|                |     |
|----------------|-----|
| Observer-Blind | Yes |
| Subject-Blind  | Yes |
| Double-Blind   | Yes |

Randomization:

Group Assignment Ratio: 2:1 randomization of two subjects who receive sildenafil to one subject who receives placebo.

Concurrent Control:

No other treatments for lymphatic malformation will be allowed except antibiotics and/or surgical drainage if the lesions become infected. Treatment for recurrent infections in the lymphatic malformation will be allowed and documented during the trial. Concurrent medications will be documented. Subjects who require sclerosing agents or excisional surgery of their lymphatic malformation will be withdrawn from the trial.

Variable(s): PRIMARY: Change in lesion volume over twenty weeks of the test medication as evaluated by MRI examination. Comparison of placebo to sildenafil treated subjects.

SECONDARY: Change in lesion volume estimated using a soft tape measure to measure the length, width, and hemispheric measurement of each of the lymphatic malformations. (Berk, Berk et al. 2011) Completion of the form *Lymphatic Malformation Measurements*.

Subject's evaluation of the change in lesion clinical characteristics from baseline to 20 weeks by examining decreased discomfort, texture or thickness, distortion of normal anatomy or overall change obtained in the subject's

completion of *Subject's Assessment of Lymphatic Malformation Change* form.

Physician's evaluation of the lesion clinical characteristics on the day of the visit. This includes color, tenseness and texture, superficial component, deep component, and distortion of anatomical landmarks. This requires completion of the *Lymphatic Malformation Assessment* form for each LM site.

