Physician's evaluation of the change in lesion clinical characteristics from baseline, such as change in texture or thickness, change in distortion of normal anatomy, and over change in lesions. This requires completion of the *Lymphatic Malformation Assessment of Change* form for each LM site.

Comparison of LM volume from MRI assessment to Body Surface Area (BSA) measurements before and after 20 weeks of sildenafil.

Blinded physician observer scored evaluation of clinical photographs taken prior to the initial dose of sildenafil or placebo and at the 20 week visit prior to the unblinding. Subjects who receive placebo and then enter the 20 week open label continuation will have additional photographs taken after 20 weeks of sildenafil.

Presence, frequency or absence of infection during trial.

Relationship of response to sildenafil to previous infections, sclerotherapy or surgery.

**SAFETY:** Adverse events and frequency of lesion infections.

Adverse Events: Both volunteered and elicited.

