A second method to evaluate the volume of the MRI will be done in a blinded manner by a pediatric radiologist, assisted by a pediatric radiology fellow. We will use segmentation to identify the surface area demonstrating LM involvement of multiple planes though the lesion. By calculating the surface area of multiple planes and knowing the distance between planes, the volume of the LM can be calculated. This is called segmentation analysis. The research radiologist and fellow will evaluate multiple MRIs in groups at the same time, unaware of the date or the subject, therefore blinded to treatment, placebo, or pretreatment. This evaluation will be blinded in order to eliminate the bias of knowing who the subject is in the study. Although this is a research procedure, the results will be reported in the subjects Radiology Report in the Medical Record as an addendum. It will be signed by the research radiologist. This evaluation will be available several weeks after the subject completes the 20 weeks of sildenafil and/or placebo. The MRI will be read and the data recorded by the research radiologist without knowledge of the date the MRI was done. Once the data is collected and recorded, the research radiologist will learn name of the subject and the date of the MRI in order to attach the correct volume calculation to the correct MRI when placing the volume data in the Medical Record.

The volume data on the subject's LM(s) relative to the subject's BSA will then also be evaluated for any changes. Since all subjects will be children under 10 years old, using the BSA measurement may help to adjust our volume assessment to accommodate the amount that a subject has grown over the course of the course of treatment.

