#### **10.2.1. Primary Efficacy**

Summary statistics will be determined for change in lesion volume by a radiologist blinded to the time of the MRI and whether the patient was on treatment or placebo. The initial MRI will be compared to the MRI after 20 week of sildenafil or placebo. If the subject on placebo elects to take sildenafil for 20 weeks the MRI used for comparison after 20 weeks of sildenafil will be the MRI taken after 20 weeks of placebo.

We will include in the interim analysis information about the characteristics of LMs. We will do a sub-analysis looking at specifics of location, lesion type (microcystic, macrocystic, or mixed and percent macrocystic), as well as previous procedures, infections or other interventions. If this process documents characteristics of lesions that do or do not respond to sildenafil, we will reconsider our study entry criteria and submit a protocol amendment for the IND and this grant, focusing more on specific characteristics of which type of lesion a subject should have in order to be enrolled in the trial.

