#### **10.2.2. Secondary Efficacy**

The secondary efficacy variables will be change from baseline and at visits four weeks twelve weeks, twenty weeks and 32 weeks.

These will include the changes in the soft tape measurements of the lesion by comparing the measurements of length, width, and hemispheric measurement. The volume of the lymphatic malformation will be estimated based on these measurements.

Statistical analysis of the *Subject's Assessment of Lymphatic Malformation Change* form. This will give data on the subject's evaluation of the change in lesion clinical characteristics from baseline, such as decreased discomfort, texture or thickness, distortion of normal anatomy or overall change by correlating the data obtained in the subject's completion of *Subject's Assessment of Lymphatic Malformation Change* form.

Statistical analysis of the *Lymphatic Malformation Assessment* form for each LM site. This will give data on the physician's evaluation of the lesion clinical characteristics on the days of the visits. This includes color, tenseness and texture, superficial component, deep component, and distortion of anatomical landmarks.

Statistical analysis of the *Lymphatic Malformation Assessment of Change* form for each LM site. This will give data on the physician's evaluation of the change in lesion clinical characteristics from baseline, such as change in texture or thickness, change in distortion of normal anatomy, and over change in lesions.

Change in LM volume from MRI assessments in relation to BSA will also be carried out. REDCap calculates the BSA from height and weight measurements at each visit. Since growth can be non-linear, relating the LM volume to a subject's BSA may help to explain why a small change to the LM (by MRI volume analysis) is assessed as moderate by the investigator and parents of the subject (i.e., the LM may have stayed the same size but the child grew quickly, so the LM appears smaller by visual assessment).

The digital photographs of each lymphatic malformation in this study will be acquired by the site investigators. At least two digital photographs of the lymphatic malformation will be acquired for each patient at each scheduled study visit, a front-on view and a side-on view. See Section 7.4.4. The clinical photographs evaluated by blinded observers in a blinded manner by physicians not associate with this trial. The observers of the

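### The MRI volume/BSA endpoint has no stated placebo comparison, and in growing children its before/after change has a no-effect value that is not zero and varies with age

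*Combined protocol and SAP*

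**What the plan says.** The Synopsis (Variables, Secondary) lists "Comparison of LM volume from MRI assessment to Body Surface Area (BSA) measurements before and after 20 weeks of sildenafil". Placebo is not mentioned there. It is mentioned for the primary variable, MRI lesion volume, where the Synopsis adds "Comparison of placebo to sildenafil treated subjects", and again in the photograph item that follows the BSA line.

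The body is less restrictive but no more specific. Section 6.1 says "The volume data on the subject's LM(s) relative to the subject's BSA will then also be evaluated for any changes", and gives as the reason that "using the BSA measurement may help to adjust our volume assessment to accommodate the amount that a subject has grown". Section 10.2.2 says "Change in LM volume from MRI assessments in relation to BSA will also be carried out". Neither names a comparator, model or test. Section 10.2.2 goes on to explain that the ratio may account for clinical ratings that look better than the MRI result, because "the LM may have stayed the same size but the child grew quickly, so the LM appears smaller by visual assessment".

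The data for a controlled comparison are already planned. Section 10.2.1 states "The initial MRI will be compared to the MRI after 20 week of sildenafil or placebo", and Section 10.2.2 states "REDCap calculates the BSA from height and weight measurements at each visit".

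**The concern.** A ratio of lesion volume to BSA moves when either part moves. Subjects are between 6 months and 10 years old and the MRIs are about 20 weeks apart, so BSA will rise in nearly all of them. A change in the ratio within a treated child is then a mixture of lesion change and body growth, and nothing inside a sildenafil-only comparison separates the two. A lesion that stays still gives a falling ratio. A lesion that grows with the child gives a rising one, because volume scales with length cubed and BSA with length squared.

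If the Synopsis line were followed as written, a fall after sildenafil could be reported as a response when the children had only grown, or a real effect could be hidden by lesion growth. Because the shift is largest in the youngest children, it could also pass for an age-dependent drug effect. The wording would also admit the open-label courses of former placebo subjects as further uncontrolled pairs: Section 10.2.1 takes their post-placebo MRI as the starting scan.

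**Working it through.** The plan gives no figure for this endpoint, and no growth rate, SD, alpha or power anywhere, so there is nothing of its own to reproduce. From the documents: age 6 months to 10 years, minimum weight 8 kg, 20 weeks of blinded treatment, 2:1 allocation, up to 60 subjects (40:20), with a goal of 40 completers (about 27:13). Growth and SD below are assumptions.

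**Formulas.** Let BSA rise by a fraction g.
- Unchanged lesion: change in volume/BSA = 1/(1+g) - 1 = -g/(1+g).
- Lesion growing in proportion to body weight: change = (weight ratio)/(BSA ratio) - 1.
- BSA (Mosteller) = sqrt(kg × cm / 3600).

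**Illustrative children over 20 weeks (assumed sizes).**

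| Child | Start → end | BSA | BSA change | Unchanged lesion | Weight-proportional lesion |
|---|---|---|---|---|---|
| Infant | 8.0 kg, 67 cm → 9.7 kg, 74 cm | 0.386 → 0.447 | +15.7% | -13.6% | +4.8% |
| About 2 years | 12.2 kg, 87 cm → 13.2 kg, 91 cm | 0.543 → 0.578 | +6.4% | -6.0% | +1.7% |
| About 5 years | 18.5 kg, 109 cm → 19.4 kg, 111.5 cm | 0.748 → 0.775 | +3.6% | -3.4% | +1.2% |
| About 9 years | 28 kg, 133 cm → 29.3 kg, 135 cm | 1.017 → 1.048 | +3.1% | -3.0% | +1.5% |

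Infant, worked: the BSA ratio is 1.157, so an unchanged lesion gives 1/1.157 - 1 = -13.6%. The weight ratio is 9.7/8.0 = 1.2125, and 1.2125/1.157 - 1 = +4.8%.

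**Range in g.** For an unchanged lesion, g of 2%, 3%, 5%, 8% and 12% gives -2.0%, -2.9%, -4.8%, -7.4% and -10.7%. If volume instead scales as BSA to the power 1.5, g of 3%, 5% and 12% gives +1.5%, +2.5% and +5.8%.

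**What a test would do with an unchanged lesion and no drug effect.** The plan attaches no test to this ratio, so this is illustration only. It assumes a one-sample t test of the log ratio at two-sided 0.05, with mean change -ln(1+g).

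| n on sildenafil | SD of log ratio | g = 3% | g = 5% | g = 8% |
|---|---|---|---|---|
| 40 | 0.20 | 0.149 | 0.325 | 0.660 |
| 40 | 0.40 | 0.074 | 0.117 | 0.221 |
| 27 | 0.20 | 0.115 | 0.231 | 0.486 |

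The entries are false-positive rates. A two-sample comparison with placebo, simulated 50,000 times at SD 0.20 with the same g in both arms, gives 0.049 to 0.051 for 40:20 and 27:13.

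**Why the comparison with placebo works.** On the log scale, the between-arm difference in change of volume/BSA equals the difference in log-volume change minus the difference in log-BSA change. If sildenafil does not alter growth, the second term has expectation zero under randomisation, whatever the natural course of the lesion.

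**The case against.** The strongest reply has four parts.

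*The restriction to sildenafil rests on one Synopsis line.* A reader might infer that the plan confines the BSA analysis to treated subjects. The documents do not support that: Sections 6.1 and 10.2.2 carry no such limit, and Section 10.2 evaluates for efficacy everyone who receives study medication. Several other secondary variables also lack a stated contrast between arms. This stands as to scope. It does not supply the missing comparison. The linear mixed model in Section 7.4.3 does compare placebo with sildenafil, but it sits in the tape-measurement text and does not mention BSA.

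*The ratio is mainly explanatory.* Section 10.2.2 uses growth to explain why a lesion may look better than its MRI volume suggests, so the sponsor knows of the artefact. Section 11 describes the study as exploratory and descriptive, and no success rule is tied to the ratio. This also stands. It would go too far to say that the plan presents normal growth as a drug effect.

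*The direction is not fixed.* A reader might infer that, with no drug effect, this endpoint must show improvement. That holds only if untreated lesions stay the same size. The documents give no natural growth rate, and Section 3.1 notes that deeper lesions come to notice as they enlarge.

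*Randomisation is not a full cure.* Growth cancels between arms only in expectation. The assumed shift for an unchanged lesion differs more than fourfold across the age range (13.6/3.0 = 4.5), and the placebo arm is small: 20 if 60 enrol, and 5 at the first interim analysis. In addition, Sections 5.1 and 5.2 accept an MRI up to six months before screening, so BSA from the Baseline visit may not belong to the date of the scan. Both points are right, and the remedy has to deal with them.

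**Conclusion.** The point holds in this form. The only contrast written down for the volume/BSA endpoint is a before/after one on sildenafil; the body neither limits the endpoint to sildenafil nor names a placebo comparison. The no-effect value of that change is not zero and varies with age: about -3% to -14% for an unchanged lesion, and about +1% to +5% for one that keeps pace with body weight. These sizes rest on assumed heights and weights, and the -14% end describes a fast-growing infant at the 8 kg entry limit. That the ratio mixes growth with lesion change is algebra and needs no such assumption. The sign of the shift depends on the lesion's natural course, which the documents do not give, so neither a fall nor a rise after sildenafil is evidence about the drug without the placebo arm. The matter is confined to a secondary, partly explanatory variable. The primary endpoint is not affected.

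**What to change.** In the Synopsis and Section 10.2.2, define the endpoint as percent (or log) change in MRI volume/BSA from the initial MRI to Week 20 of the blinded period, compared between the randomised sildenafil and placebo arms and adjusted for age. Choose one scale and state it. Take BSA from the height and weight recorded closest to each MRI date, which matters where a scan made before screening serves as baseline.

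Report the unadjusted change in MRI volume beside it, so that a reader can see whether the lesion or the denominator moved. Label ratios before and after sildenafil, including those from the open-label period, as descriptive.

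MRI, height, weight and age are already collected in both arms, so no visit, scan or subject is added. The cost is slightly more analysis work. The small placebo arm will limit the precision of the comparison.

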### 3. INTRODUCTION

#### 3.1. BACKGROUND

**Lymphatic malformations** (LMs) are uncommon, congenital vascular anomalies that arise due to developmental dysplasia of the lymphatic network in utero.(Blei 2008) LMs are equally rare independent of sex or race.(Redondo, Aguado et al. 2011) About 65% of LMs are detected at delivery, 80% by 1 year of age, and 90% by 2 years of age

emphasizing their childhood expression.(Redondo, Aguado et al. 2011) The deeper ones may not be initially noticed but will become recognized as they increase in size or become infected. Although histologically benign, they are often locally invasive and affect the skin and soft tissues, as well as nerve, muscle or bone in some cases. Cystic hygromas are a specific type of congenital malformations of the lymphatic system that are commonly on the posterior neck. (Gallagher, Mahoney et al. 1999) They occur in about one in 1,775 live births (Howarth, Draper et al. 2005) to one in 2667 live births (Fisher, Partington et al. 1996) making them truly an orphan disease. The incidence may be higher as they can be associated with other fetal abnormalities resulting in spontaneous or induced abortions.(Fisher, Partington et al. 1996) In one series of 17 live born infants with cystic hygroma, 15 survived the first year of life yielding a survival rate of 88%.(Fisher, Partington et al. 1996) Lymphatic malformations often have considerable morbidity, associated with infection, bleeding and airway or vision obstruction as well as significant psychosocial concerns. (Greene, Perlyn et al. 2011) When present on the extremities, they often bleed with physical activity, may inhibit movement and ambulation, and are at times painful.

### **3.2. RATIONALE**

Recently propranolol, a commonly used medication for hypertension, has been shown to have impressive efficacy in the treatment of infantile hemangiomas. (Leaute-Labreze, Dumas de la Roque et al. 2008) The new indication for this “old” drug was discovered when two children with infantile hemangiomas and heart problems (one with cardiac myopathy, the other with increased cardiac output) were placed on propranolol. Unexpectedly, their hemangiomas involuted quickly and dramatically after the initiation of the medication. To verify the effect of propranolol on hemangiomas, 9 other infants with infantile hemangiomas but no heart disease were then treated with propranolol, and all had rapid resolution of their infantile hemangiomas. (Leaute-Labreze, Dumas de la Roque et al. 2008) In addition, propranolol was well-tolerated and has a better side effect profile than oral corticosteroids, the traditional treatment for problematic hemangiomas. Additional studies have verified that hemangiomas respond quickly to propranolol, and the medication has been used successfully to treat not just infantile hemangiomas affecting the skin but of the airway and liver, as well as those complicated by ulceration.(Frieden and Drolet 2009; Sans, de la Roque et al. 2009; de Graaf, Breur et al. 2011; Fuchsmann, Quintal et al. 2011) After our own striking and serendipitous observation, we are hopeful to verify the effect of sildenafil on LMs. If successful, sildenafil has the potential to have just as large an impact in the treatment of LMs as propranolol has with hemangiomas. There is no effective nonsurgical treatment for this orphan disease.

### **3.3. OBJECTIVE**

The objective in this study is to assess the safety and efficacy of sildenafil in reducing the volume and symptoms of lymphatic malformations when administered to subjects who have lymphatic malformations greater than 3 cm in diameter.

## 4. TEST MEDICATION

### 4.1. IDENTIFICATION

Test medication: Sildenafil (Revatio®) 20 mg tablets or suspension

Control Medication: Placebo or suspension resembling Revatio®

### 4.2. PACKAGING AND LABELING

The test medications will consist of Sildenafil 20 mg tablets (Revatio®) and Placebo tablets that resemble Revatio®. These medications will be shipped in bulk containers to the Lucile Packard Children's Hospital (LPCH) Pharmacy where they will be stored.

Each bottle will be labeled in accordance with Good Manufacturing Practice and will include the following information:

- Study Acronym Name
- Unique alpha-numeric identifier (Lot number)
- Storage requirement
- Investigational use and appropriate caution statements
- Sponsor identification
- Unique subject ID

The LPCH Pharmacy will dispense the Revatio® or Placebo in bottles labeled with the subjects identification information based upon the randomized code. The LPCH Pharmacist will compound an extemporaneously prepared oral suspension from Revatio® 20mg tablets or placebo tablets, depending on subject's preference.

Pharmacy staff will know if the subject is receiving Placebo or Revatio®. Depending on subjects weight, the study pharmacist will formulate study drug into an oral suspension for 2.5mg per ml dosing volume.

Subjects who weigh 8kg – 20kg will receive a 4-week supply 10mg/4ml TID, and the treatment will be compounded into a 480ml dosing volume, and then transferred to four bottles of 120 ml each.

Subjects weighing more than 20kg will receive a 4-week supply 20mg/8ml TID. The subject and the research physician will be blinded to Placebo or Revatio® until completion of the 20 week study visit. The code will also be broken in the situation of a Serious Adverse Event.

### 4.3. TEST MEDICATION ACCOUNTABILITY PROCEDURES

When a delivery of test medication is received at the investigational site, the Pharmacist, or a member of their staff specifically authorized and delegated by the Investigator, will check for accurate delivery and acknowledge receipt by signing (or initialing) and dating the required documentation and returning it as instructed. The

date, time, and condition of the package should also be documented at the time of receipt. A copy of this documentation will be retained for the Investigator file.

The LPCH Pharmacist will compound Revatio® 20 mg film-coated tablets or placebo. The pharmacy instructions for compounding are listed in section [17.1](#).

The packing list will indicate the expiry date for the material. Receipt and dispensing of the study treatment will be carefully recorded on appropriate accountability forms and made available for verification at each monitoring visit.

Used medication containers will be retained until checked by study monitor, after which they will be discarded at the site. Unused medication will be accounted for at the end of the trial and appropriately discarded at the site.

For study visits conducted at non-Stanford sites, medication will be prepared in the LPCH Pharmacy and shipped directly to the subject from Stanford for each visit.

A study monitor will perform an accounting of all test medication supplies, used or unused, at the study centers.

